2.5 Outcomes

Primary Outcome

Weight gain over 8 weeks (Specific Aim 1). Weight will be measured at all follow-up time points and weight gain will be defined as grams per kilogram per day (g/kg/day).

Secondary Outcomes

Nutritional recovery by 8 weeks (Specific Aim 2). Nutritional recovery will be defined as a child having WHZ \geq -2 on two consecutive visits and no acute complication or edema for the past 7

[figure not shown]
days AND / OR MUAC of $\geq 125\text{mm}$ on 2 consecutive visits and no acute complication or edema for the past 7 days. The criteria chosen to define the recovery will be the same one we used to admit the child into the program as defined in the national guidelines:

Criteria of admission	Criteria of discharge
MUAC < 11.5cm	MUAC > 12.5cm (for 2 consecutive weeks) Sustained weight gain Clinically well
Bilateral oedema	MUAC > 12.5cm No oedema for 2 consecutive visits Clinically well
WHZ < -3 SD	MUAC > 12.5cm AND WHZ >-2 for 2 consecutive visits Clinically well

- **Weight gain over 12 weeks.** Weight will be measured at all follow-up time points and at 12 weeks after admission to the program. Weight gain will be defined as grams per kilogram per day (g/kg/day).
- **Time to recovery.** Time from enrollment to nutritional recovery (defined above) will be calculated in days by subtracting the date of enrollment from the date of nutritional recovery.
- **Nonresponse at 8 weeks.** Nonresponse will be documented if a child does not meet the criteria for nutritional recovery at 8 weeks.
- **Transfer to inpatient care.** The occurrence, date, and reason for transfer from outpatient to inpatient treatment will be recorded.
- **Mortality by 8 weeks.** Vital status will be assessed at all follow-up time points and mortality will be defined as death during the study period. Date of death will be recorded.
- **Mortality by 12 weeks.** Vital status will be assessed at all follow-up time points and mortality will be defined as death during the study period. Date of death will be recorded.
- **Clinical signs of infection.** At all follow-up time points, clinical signs of infection will be recorded, including care-giver reported experience of fever, diarrhea, vomiting, and respiratory infection/cough and clinical diagnoses made at by site personnel
- **Adverse events.** Adverse events will be reported at all follow-up time points
- **HAZ.** Height or length will be measured monthly and height-for-age z-scores will be calculated.

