9. STATISTICAL METHODS

9.1 Sample Size and Power

Specific Aim 1 We assume that inclusion of 600 children (300 randomized to each arm) will provide 80% power to detect a 15% increase in weight gain (g/kg/day) in children receiving azithromycin compared to children receiving amoxicillin at an alpha of 0.05. Assumptions for this calculation were based on the pattern of weight gain reported in a trial of routine amoxicillin for uncomplicated SAM in Burkina Faso comparing children receiving azithromycin to amoxicillin over time.¹¹ We assumed an average weight gain of 2.6 g/kg/day over 8 weeks in the amoxicillin arm, with a standard deviation of 1.7 g/kg/day, and loss to follow-up of 10%. A 16% increase corresponds to a mean difference in weight gain of 0.4 g/kg/day, or an average weight gain of 3.0 g/kg/day in the azithromycin arm.

This calculation was performed in Stata using the following command:

```
power twomeans 2.6, sd(1.7) alpha(0.05) power(0.8) n(540)
```

Specific Aim 2. Inclusion of 600 children (300 randomized to each arm) will provide 80% power to detect a 12 percentage point difference in the proportion of children achieving nutritional recovery in the azithromycin arm compared to the amoxicillin arm. Assumptions for this calculation were based on nutritional recovery reported in the amoxicillin arm of a trial of routine amoxicillin compared to azithromycin for uncomplicated SAM in Burkina Faso.¹¹ We assumed that 36% of children in the oral amoxicillin arm would achieve nutritional recovery and a loss to follow-up of 10%.

This calculation was performed in Stata using the following command:

```
power twoproportions 0.36, alpha(0.05) power(0.8) n(540)
```

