9.2 Statistical Analysis

Baseline characteristics. Characteristics of the study population collected at baseline will be summarized using frequencies and percentages for categorical variables and means and standard deviations or medians and inter-quartile ranges for continuous variables. Baseline characteristics will be compared by treatment arm using Fisher's exact test for categorical variables and t-tests or Wilcoxon rank-sum tests for continuous variables.

Specific Aim 1. The primary analysis will compare weight gain velocity (g/kg/day) between groups over the 8-week follow-up period. We will estimate mean differences and 95% confidence intervals for the difference using a linear regression model with an indicator for study group.

$$E[Y | X = x] = \beta_0 + \beta_1 X + e$$

Where:

- **Y = weight gain velocity from enrollment to 8 weeks**
- X = binary indicator for treatment group ($X=1$ for azithromycin, $X=0$ for a short course of oral amoxicillin)

- β_1 = difference in weight gain velocity between the azithromycin group compared to a short course of oral amoxicillin group
- $e \sim N(0, \sigma^2)$

Sensitivity analyses will include similar linear models to assess period-specific weight gain by group from week 0-1, 1-2, 2-4, and 4-8.

Specific Aim 2. The primary analysis will compare nutritional recovery by 8 weeks from baseline by arm. We will use log-binomial regression for this analysis to estimate the risk ratio. We will use the following model:

$$\log[P(Y = 1|X_1 = x_1)] = \beta_0 + \beta_1 X_1 + e$$

Where:

- **Y = binary indicator for nutritional recovery by 8 weeks ($Y=1$ for recovered, $Y=0$ for not recovered)**
- X = binary indicator for treatment arm ($X=1$ for azithromycin, $X=0$ for a short course of oral amoxicillin)
- e^{β_1} = relative risk of nutritional recovery in azithromycin arm compared to a short course of oral amoxicillin arm
- $e \sim N(0, \sigma^2)$

If the log-binomial model fails to converge, we will use a modified Poisson model with robust standard errors as an alternative.

Secondary outcomes.

Time to event outcomes (time to recovery and time to mortality) will be assessed visually using Kaplan-Meier curves and compared by arm using the log-rank test.

Binary outcomes will be analyzed using modified Poisson regression for rare outcomes (e.g. mortality) or log-binomial regression for common outcomes (e.g. malaria), using models similar to the one described above for Specific Aim 2.

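### Section 9.2 has no rule for zero events in one arm, where its modified Poisson analysis of mortality returns a meaningless near-zero p-value without warning

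*Combined protocol and SAP*

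**What the plan says.** Section 2.5 lists mortality by 8 weeks and mortality by 12 weeks as separate secondary outcomes: "Vital status will be assessed at all follow-up time points and mortality will be defined as death during the study period".

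Under secondary outcomes, section 9.2 states: "Binary outcomes will be analyzed using modified Poisson regression for rare outcomes (e.g. mortality"), gives common outcomes to log-binomial regression, and says both will be fitted "using models similar to the one described above for Specific Aim 2", that is, with a treatment indicator and a log link. The variance estimator is named under Aim 2: "If the log-binomial model fails to converge", then "we will use a modified Poisson model with robust standard errors as an alternative". That is the only fallback in the plan, and it leads to modified Poisson, not away from it.

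The rest of section 9.2 asks for inference at 0.05, a 95% confidence interval for every effect estimate, analysis in R, and unspecified model diagnostics. Fisher's exact test appears only for baseline comparisons. Time to mortality also gets Kaplan-Meier curves and a log-rank test. No sentence covers an arm with no events, and neither section 9.1 nor 9.2 gives an expected death rate.

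**The concern.** Modified Poisson regression takes its inference from the robust (sandwich) variance. When one arm has no events, the maximum likelihood estimate of the log risk ratio is infinite and no Wald result is meaningful. A model-based standard error shows this by becoming enormous. The robust standard error does not: it stays small and finite. The printed output is a risk ratio near zero (or very large, if the empty arm is amoxicillin), a narrow interval and a p-value that is zero for practical purposes.

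The plan gives this method to rare outcomes, which is where an empty arm is most likely. If it is followed literally, one to five deaths against none would produce a highly significant mortality effect that the data do not support. If it is not followed, the analyst must choose a replacement after seeing the deaths by arm.

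**Working it through.** **Inputs.** From the documents: 600 children, 300 per arm; 10% loss, so 270 per arm analysed; modified Poisson with robust standard errors; R; alpha 0.05, taken as two-sided. Not in the documents, and therefore assumed: the death risk, set equal in both arms and varied from 0.2% to 2%.

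**Plan's own figure, to confirm the arm size.** Section 9.1 says: "Inclusion of 600 children (300 randomized to each arm) will provide 80% power to detect a 12 percentage point difference", from 36% recovery on amoxicillin. With 270 per arm, 36% against 48% and pooled proportion 0.42:

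z = [0.12 × √270 − 1.96 × √(2 × 0.42 × 0.58)] / √(0.36 × 0.64 + 0.48 × 0.52) = (1.972 − 1.368) / 0.693 = 0.871, so power is 80.8%.

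The stated 80% is reproduced. There is no stated figure for mortality to reproduce.

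**Why the robust standard error collapses.** Take e deaths among n in one arm and none among n in the other.

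- Arm with deaths, p = e/n: the robust variance contribution is np(1 − p)/(np)² = 1/e − 1/n.
- Empty arm: the fitted mean μ is tiny and every residual is −μ, so the contribution is nμ²/(nμ)² = 1/n, however small μ becomes.
- Sum: 1/e. The robust standard error is 1/√e.
- The model-based contribution of the empty arm is 1/(nμ), which grows without limit as μ shrinks.

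**Fits in R** (default settings, 300 per arm, no deaths on azithromycin, HC0 standard error). Every fit reported convergence and none gave a warning.

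| Deaths | log RR | Robust SE | Robust Wald p | Fisher p |
|---|---|---|---|---|
| 0 vs 1 | −17.60 | 1.000 | 2.5e-69 | 1.00 |
| 0 vs 2 | −18.29 | 0.707 | 1.5e-147 | 0.50 |
| 0 vs 3 | −17.70 | 0.577 | 2.4e-206 | 0.25 |
| 0 vs 5 | −18.21 | 0.447 | prints 0 | 0.061 |
| 0 vs 6 | −18.39 | 0.408 | prints 0 | 0.030 |

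For 0 vs 1 the 95% interval for the risk ratio is exp(−17.60 ± 1.96 × 1.00), or 3.2e-9 to 1.6e-7. HC1 and HC3 are as extreme (4e-69 and 7e-69), and so is the mirror case with no deaths on amoxicillin. The model-based standard error for the same 0 vs 1 fit is 4,021 (p = 0.997). Python's statsmodels also converges silently, but stops at a log risk ratio of −20.4 with p = 2e-92. The exponent depends on the software and has no meaning.

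**How often exactly one arm is empty.** With common risk r and n per arm, the probability is 2q(1 − q), where q = (1 − r)^n. At r = 1% and n = 300, q = 0.0490 and 2 × 0.0490 × 0.9510 = 9.3%.

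| Assumed death risk | 300 per arm | 270 per arm |
|---|---|---|
| 0.2% | 49.5% | 48.6% |
| 0.5% | 34.6% | 38.3% |
| 1% | 9.3% | 12.4% |
| 1.5% | 2.1% | 3.3% |
| 2% | 0.5% | 0.9% |

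Every such table is declared significant, so each entry is a lower bound on the type I error at that risk. At 1% and 300 per arm, tables with deaths in both arms add 0.4 points, about 9.7% in all. At 2% the sum is 0.5 + 2.5 = 3.0%.

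**The case against.** Four points count against the concern.

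First, mortality has a second planned test. With deaths placed at day 28 and the other children censored at day 56 (assumed times), the log-rank p is 0.157 for 0 vs 2 and 0.083 for 0 vs 3. A reader might infer that the trial would simply announce overwhelming evidence on mortality. The documents do not support that, because a non-significant planned result would stand beside it. What remains is that the log-rank test gives no risk ratio or interval, although the plan asks for an interval for every effect estimate, and nothing says which result prevails.

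Second, the failure is not hidden from a careful analyst. A risk ratio near 1e-8 is conspicuous, the ordinary model output shows a standard error in the thousands, and section 9.2 calls for diagnostics. With no deaths in either arm, R does warn. This stands, but the diagnostics sentence names no remedy, and the choice of remedy matters: for 0 vs 3, Fisher gives 0.25, the log-rank test 0.083 under the timing above, and the likelihood-ratio test 0.041.

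Third, a reader might infer that robust Wald inference is untrustworthy whenever deaths are few. The check does not show that. With deaths in both arms the p-values stay near Fisher's: 1 vs 5 gives 0.14 (Fisher 0.22), and 1 vs 8 gives 0.049 (Fisher 0.038). At 300 per arm, false positives from such tables total 0.4% at 1% assumed mortality, 2.5% at 2% and 3.7% at 3%. Interval coverage was not examined. Nothing here supports a minimum event count above zero.

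Fourth, no section gives a death rate. Section 1.1 describes severe acute malnutrition as carrying high mortality; section 2.2 restricts entry to children without complications needing inpatient care; section 9.2 itself calls mortality rare. None of these fixes the rate at or below 1%.

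**Conclusion.** The gap is real and confined to one situation: no events in exactly one arm. There the prescribed analysis gives a p-value and interval with no inferential meaning, and R reports convergence. That result is arithmetic and holds for any sample size.

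Its practical weight depends on an unstated mortality rate. Under equal risks at the planned size, the test exceeds its nominal 5% error at about 1% mortality or below, and the problem is negligible at 2 to 3%. Any other binary outcome analysed this way has the same exposure if one arm is empty.

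It would be wrong to infer that the primary result is at risk. Weight gain is analysed by linear regression and is unaffected. The point concerns a secondary outcome with a partial safeguard. It deserves correction because a stated rule gives a wrong answer in a foreseeable case and the remedy is cheap.

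**What to change.** Add one sentence to section 9.2 under secondary outcomes: for mortality by 8 weeks, mortality by 12 weeks and any other binary outcome, if either arm has zero events, the robust Wald result will not be reported; counts by arm, Fisher's exact p-value and the risk difference with an exact or score 95% interval will be reported instead. Choose the interval method when the sentence is written. Keep modified Poisson whenever both arms have events.

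The cost is small. Fisher's test is slightly conservative, and the effect measure becomes a risk difference in that case. Design, data collection and sample size do not change.

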2. STUDY DESIGN

This randomized controlled trial is designed to determine the effect of administration of azithromycin compared to amoxicillin as part of the treatment of uncomplicated SAM in children aged 6-59 months on weight gain and nutritional recovery. We will randomize children presenting to Taimaka-run nutritional programs at health centers in Gombe State, Nigeria to a single dose of oral azithromycin or a short course of oral amoxicillin upon admission into the program. Apart from the administration of antibiotics, all children will receive standard outpatient treatment for uncomplicated SAM as specified in the guidelines of the government of Nigeria, which includes therapeutic feeding with RUTF. Enrolled children will be followed weekly at each routine clinic follow-up visit up until nutritional recovery. All enrolled children will return for a final study visit at 8 weeks following enrollment. Anthropometric and vital status data will be collected at each follow-up visit. Weight gain and nutritional recovery over the 8-week study period will be compared by arm as a primary outcome and at 12 weeks as a secondary outcome.

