Anthropometric assessments will be analyzed using linear models as described for Specific Aim 1, with correction for baseline values. For anthropometric assessments, z-scores will be calculated based on the 2006 WHO Child Growth Standards. Anthropometric z-scores will be analyzed as continuous variables and secondary analyses will explore categorization.

All analyses will be intention-to-treat. A significance level of 0.05 for inference and 95% confidence intervals will be reported for all effect estimates. All analyses will be conducted using R (R Foundation for Statistical Computing, Vienna, Austria). For all models, model diagnostics will be conducted to assess appropriate fit.

Missing data.

If $\leq 10\%$ of enrolled children is missing outcome data, complete case analyses will be conducted. If $> 10\%$ of enrolled children are missing outcome data, inverse probability weighting will be used to weight complete cases by the inverse of an estimate of the probability of an outcome being observed as a sensitivity analysis. Weights will be constructed with the following

baseline characteristics chosen as factors likely to predict follow-up: SES, distance from health center, WHZ, and MUAC.

REFERENCES

2. Page AL, de Rekeneire N, Sayadi S, et al. Infections in children admitted with complicated severe acute malnutrition in Niger. *PLoS One*. 2013;8(7):e68699. doi:10.1371/journal.pone.0068699

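### The plan does not say when recovery by 8 weeks is missing; on the likely reading, complete-case analysis selects on the Aim 2 outcome, and the risk ratio suffers materially if loss differs by arm

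*Combined protocol and SAP*

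**What the plan says.** The Aim 2 outcome in Section 9.2 is a "binary indicator for nutritional recovery by 8 weeks", analysed by log-binomial regression to give a risk ratio. Section 2.5 builds recovery from two consecutive qualifying visits.

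Section 2 sets the follow-up: "Enrolled children will be followed weekly at each routine clinic follow-up visit up until nutritional recovery". It adds: "All enrolled children will return for a final study visit at 8 weeks following enrollment". The week-8 visit is therefore planned for children who have already recovered as well.

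Under Missing data in Section 9.2, if no more than 10% "of enrolled children is missing outcome data, complete case analyses will be conducted". Above 10%, "inverse probability weighting will be used to weight complete cases", but only as a sensitivity analysis, so the complete-case result stays primary at any level of loss. The weights use "baseline characteristics chosen as factors likely to predict follow-up: SES, distance from health center, WHZ, and MUAC".

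On children who do not recover, Section 2.5 says: "Nonresponse will be documented if a child does not meet the criteria for nutritional recovery at 8 weeks". No section says how Aim 2 classifies a child who recovers and then misses week 8, a child who leaves unrecovered, or a child who dies unrecovered.

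**The concern.** Recovery by 8 weeks is cumulative. Once the criteria have been met and recorded, Y=1 is known whatever happens next. For a living child, Y=0 is known only after follow-up to week 8. The natural way to apply the missing-data rule is to keep a child who recovers at week 3 and then stops coming, and to drop a child who stops coming unrecovered at week 4. Two children who leave for the same reason are then treated differently because of their outcome.

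Baseline weights do not correct this. Whether a leaver stays in the analysis depends on recovery status at the time of leaving, which is not in the weight model. The missing week-8 weights of Aim 1 do not have this asymmetry.

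At stake are the recovery proportion reported for each arm and, if the arms lose children at different rates, the Aim 2 risk ratio and its type I error.

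**Working it through.** **Inputs from Section 9.1:** 36% recovery on amoxicillin, a 12-point difference (so 48% on azithromycin), 10% loss, two-sided alpha 0.05, 600 enrolled and 540 analysed.

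**The plan's own figure.** With 270 per arm and 36% versus 48%, power is 80.8%, against 80% stated. The design figure reproduces. The true risk ratio is 0.48/0.36 = 1.333.

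**Random loss, likely reading.** Let p be the true 8-week recovery risk and d the share of children who leave before week 8, independently of outcome. Let g be the share of eventual recoverers among those leavers who go before their recovery is recorded. The documents do not give g, so I show 0 to 1.

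Complete-case risk = p(1 − dg) / [p(1 − dg) + (1 − p)(1 − d)]

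For example, with p = 0.36, d = 0.10, g = 0: 0.36 / (0.36 + 0.64 × 0.90) = 0.36/0.936 = 38.5%.

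Equal loss, d = 10% in both arms:

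| g | Amoxicillin (true 36%) | Azithromycin (true 48%) | Risk ratio |
|---|---|---|---|
| 0 | 38.5% | 50.6% | 1.316 |
| 0.5 | 37.3% | 49.4% | 1.325 |
| 1 | 36.0% | 48.0% | 1.333 |

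The largest overstatement is 50.6 − 48.0 = 2.6 points. The largest attenuation is 1 − 1.316/1.333 = 1.3%. With no true difference, both arms shift equally: the risk ratio is 1.000 and type I error is 5.0%.

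Unequal loss, true recovery 36% in both arms, 300 randomised per arm, d = 5% on azithromycin and 15% on amoxicillin:

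| g | Azithromycin | Amoxicillin | Risk ratio | Type I error | Overall missing |
|---|---|---|---|---|---|
| 0 | 37.2% | 39.8% | 0.934 | 9.8% | 6.4% |
| 0.5 | 36.6% | 38.0% | 0.964 | 6.3% | 8.2% |
| 1 | 36.0% | 36.0% | 1.000 | 5.0% | 10.0% |

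Swapping the arms gives 1.071 and 1.037. At 8% versus 12%, the null risk ratio is at most 2.8% from 1 and type I error at most 5.8%.

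**Worst case: no lost child would have recovered.** With L the share lost, the observed risk is p/(1 − L), so the risk ratio is multiplied by (1 − L on amoxicillin)/(1 − L on azithromycin).

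- 8% lost on azithromycin, 12% on amoxicillin: 0.88/0.92 = 0.96; type I error 7.1%.
- 5% on azithromycin, 15% on amoxicillin: 0.85/0.95 = 0.895; type I error 18.4%. The design risk ratio of 1.333 would be reported as 1.333 × 0.895 = 1.19.

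**The trigger.** Overall missing is 6.4% to 10% in every 5% versus 15% case above. None exceeds 10%, so the weighted sensitivity analysis would not be run. A threshold pooled over arms cannot see the imbalance.

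**What censoring does.** In a simulation with random dropout (constant weekly hazards, recovery possible from week 2, 12% leaving, 10.3% lost unrecovered), the true risk is 35.9%. Complete case gives 37.1%, counting leavers as not recovered gives 33.3%, and the Kaplan-Meier 8-week risk gives 35.9%. In the worst case with 5% versus 15% loss and exits assumed spread over weeks 1 to 7, censoring gives 37.1% versus 39.8%, a risk ratio of 0.93. That is closer to 1 than 0.895, but the null is not restored. Counting leavers as not recovered gives 1.00 there.

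**The case against.** The strongest objection is that the plan does not write down the classification used here. Two others fit its text. Missing could mean no week-8 visit, whatever the earlier status, since that visit is planned for everyone. Or a child who leaves unrecovered could count as a nonresponder, which sits well with the nonresponse definition and with the statement that all analyses are intention-to-treat. Neither biases the risk ratio under equal random loss. This stands: the classification above is the likely reading, not a stated rule.

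Three stronger readings are tempting, and the documents do not support them.

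- A reader might infer that children who die unrecovered are dropped. Sections 2.5 and 3.6 record vital status and date of death, so their outcome is known, and nothing says they are excluded.
- A reader might infer that the Aim 2 comparison is biased even when dropout is random. That holds for the arm proportions. The planned estimand is the risk ratio, which hardly moves when random loss is equal.
- A reader might take 18% as the expected type I error. It needs both a threefold difference in loss and no recoveries among those lost. That is ordinary informative dropout, and it would also bias a rule requiring the week-8 visit. The documents give no basis for such a difference, and caregivers are masked with a placebo syrup.

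It is also fair to say that time to recovery is already planned with Kaplan-Meier curves and a log-rank test, where early leavers can be censored. But that analysis does not produce the Aim 2 risk ratio and does not replace the complete-case rule.

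**Conclusion.** The point holds in a limited form. The plan leaves the Aim 2 outcome undefined for children who leave or die before week 8, and the likely application of its complete-case rule selects on the outcome in a way that baseline weighting does not correct.

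Under equal random loss near the planned 10%, this affects the descriptive proportions and has little effect on the comparison. The risk ratio is at material risk only if loss differs by arm. At 5% versus 15% random loss, the 4 to 7% shift applies when g is 0.5 or less and disappears at g = 1; the 0.90 result is a worst case. These loss patterns and the values of g are assumptions, not figures from the documents.

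This is more than a missing definition. The readings give different analysis sets, the choice could be made after the data are seen, and the weekly data already support a better estimator. It should be changed before analysis.

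**What to change.** Replace the complete-case rule for Aim 2 with the following.

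1. Keep all randomised children. Count a recorded recovery as Y=1 whether or not the child attends week 8, and a child known to have died unrecovered as Y=0.
2. Estimate 8-week recovery by arm from the weekly visits with the Aalen-Johansen estimator, censoring unrecovered leavers at the last attended visit and treating death as a competing event. Report the risk ratio and risk difference with bootstrap 95% confidence intervals.
3. Always report alongside it the planned log-binomial model with leavers counted as not recovered. Each analysis covers a weakness of the other. Censoring is only partly protective if loss is informative. The not-recovered rule is off when loss is random but unequal: at g = 0.5 and 5% versus 15%, 0.36 × 0.975 = 35.1% versus 0.36 × 0.925 = 33.3%, a null risk ratio of 1.05.
4. Report loss before recovery by arm, whatever the pooled percentage missing.

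The cost is SAP wording and a few lines of R, with no new data. The downsides are that the censoring-based estimate assumes independent censoring, and that the log-binomial complete-case risk ratio is no longer the only Aim 2 result.
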